## 9.6 Per-Protocol Analysis / Protocol Violations

Secondary per protocol (PP) analyses will be undertaken to assess the robustness of ITT analyses. Per protocol analyses will exclude patients who turned out not to have epilepsy, patients who were lost to follow up or for whom there is inadequate data to determine if they reached the primary endpoint, and all patients who took a different AED from the drug to which they had been randomised, before reaching the primary endpoint. Patients who were enrolled in EpiNet-First Trial 1 who turned out not to have focal seizures will be excluded from the PP analysis; similarly, patients who were enrolled in EpiNet-First Trial 2 or Trial 3 who turned out to have focal seizures (even if these evolved into generalised seizures) will also be excluded from the PP analysis. However, all patients who were included in EpiNet-First Trial 4 or Trial 5 will be included in the PP analysis if they had epilepsy, even if the exact nature of the seizures became clearer during the course of the trial.

The decision regarding which patients to exclude from the PP analysis will be made by the Trial Steering committee, who will be blinded to the treatment allocation and outcome data for each patient.

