# **Rationale**

There are numerous AEDs now registered for use in new onset epilepsy. We have chosen to study lamotrigine, carbamazepine and levetiracetam as they are widely used and generally well tolerated.

The SANAD-1 trials compared 5 AEDs in new onset epilepsy(9, 10). The authors concluded that lamotrigine was the drug of choice for patients with focal seizures, since it was more effective than gabapentin, oxcarbazepine and topiramate, and was better tolerated than carbamazepine. However, this conclusion has been challenged, and many experts still regard carbamazepine as the drug of choice for patients with focal seizures(11-13). Many of the current EpiNet investigators have informed us that carbamazepine is still regarded as the drug of first choice for patients with focal seizures in their countries. For these reason, the EpiNet-First trial 1 will include arms for both carbamazepine and lamotrigine.

Levetiracetam is a well established antiepileptic drug, and is being increasingly used as a first line treatment for children and adults with focal onset seizures (14, 15). A Cochrane review of 11 short term randomised placebo controlled add-on trials in patients (n=1861) with drug refractory focal onset seizures demonstrated efficacy and tolerability when levetiracetam is used as an add-on treatment (16).

Levetiracetam has also been assessed as monotherapy for patients with focal onset seizures. A short term trial (576 patients) comparing levetiracetam and carbamazepine monotherapy in patients with focal onset seizures found no difference in terms of the

proportion of patients that were seizure free for 6-months (17). The results met an *a-priori* definition of non-inferiority, and the drugs were similar in terms of tolerability. However, the duration of follow-up in this trial is too short to provide information about long-term seizure control, and the trial did not provide quality of life or health economic data. A second industry-sponsored un-blinded trial (the KOMET trial) compared levetiracetam with physicians' choice of carbamazepine (n=992) or valproate (n=696)(18). Although this trial recruited 1688 patients, they were only followed up for a maximum of 12 months, so longer term seizure control could not be assessed. For patients with focal onset seizures levetiracetam and carbamazepine had similar time to treatment failure rates, while time to first seizure suggested an advantage for carbamazepine.

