#### 5.2 Exclusion Criteria

Patients with the following characteristics will be excluded from the trial:

- a) Seizures provoked by alcohol or recreational drugs;
- b) Acute symptomatic seizures (e.g. acute brain haemorrhage or brain injury);
- c) Only absence seizures;
- d) Is thought to have psychogenic non-epileptogenic seizures
- e) Has ever been treated with an antiepileptic for more than one week;
- f) Known progressive neurological disease (e.g. known brain tumour).

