#### 7. TRIAL TREATMENTS

#### 7.1 Introduction

EpiNet-*First* comprises five randomised controlled trials run in parallel. Depending on the specific trial, patients will be randomised to receive either levetiracetam, lamotrigine, carbamazepine or valproate.

Randomised treatment should begin within 7 days of randomisation. The research team should ensure that any delay before starting the trial treatment does not impact on the well-being of the participant. Assessments that should be carried out prior to the start of the randomised treatment are detailed in sections 6 and 8.

All treatments will be prescribed and issued as per routine practice. Generic versions of AEDs can be prescribed, if these are routinely used in a particular centre. Specific details regarding which version of an AED is used will be recorded.

If a patient has already been commenced on an AED, he can only be recruited for any of the EpiNet First trials if:

- he/she has taken the AED for 7 days or less;
- he/she agrees to be randomised to one of the treatment arms for the trial for which the patient is eligible. (In some circumstances, it may be possible for the patient to be randomised to the drug which he/she is already taking.)
- the investigator considers that it is appropriate to include the patient in the trial.

In these circumstances, if a patient is randomised to another AED, the original AED should be withdrawn according to the investigator's standard clinical practice. In most circumstances, since the patient will have used the drug for only a few days, it will be appropriate to discontinue the AED immediately. The new AED (to which the patient has been randomised) will be introduced according to routine clinical practice. If appropriate, the two drugs can be overlapped for a brief period. Full details including the dates on which the original AED was commenced and discontinued, and the dose used, should be recorded in the EpiNet record.

If a patient is randomised to the same AED that he / she was already taking, the drug should simply be continued and/or increased according to routine practice. The date on which the patient started the drug should be recorded in the EpiNet record, even if that date is earlier than the date of randomisation. Outcome data will be calculated from the date of randomisation.

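### The per-protocol rule on taking a different AED does not exempt the short prior AED use and overlap that section 7.1 permits, so compliant patients can be dropped or kept by allocation alone

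*Protocol*

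**What the plan says.** Section 9.6 lists the per-protocol exclusions. One of them covers "all patients who took a different AED from the drug to which they had been randomised, before reaching the primary endpoint". It does not say when the period begins and does not refer to section 7.1.

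Section 7.1 allows a patient already on an AED to enter if "he/she has taken the AED for 7 days or less". Exclusion criterion 5.2(e) agrees, since it bars only a patient who "Has ever been treated with an antiepileptic for more than one week". Section 7.1 then treats two cases differently:

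- Allocated a different drug: "if a patient is randomised to another AED, the original AED should be withdrawn", and "If appropriate, the two drugs can be overlapped for a brief period".
- Allocated the drug already in use: "If a patient is randomised to the same AED that he / she was already taking, the drug should simply be continued".

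It also requires the start and stop dates of the earlier drug to be recorded, and adds: "Outcome data will be calculated from the date of randomisation".

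Section 9.1 describes the per-protocol set in another way: randomised patients who took the study drug prescribed and had no major protocol violations.

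**The concern.** A per-protocol set is meant to leave out patients who departed from the protocol. Here the rule also reaches patients who followed it exactly. For someone who entered on a trial drug, this exclusion is settled by the arm drawn: it cannot apply in the arm of that drug, and it can apply in every other arm. It reflects neither poor adherence nor response to treatment.

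The mix of starter drugs may well be uneven. The Trial 1 rationale in section 2.2 reports many investigators saying that "carbamazepine is still regarded as the drug of first choice for patients with focal seizures in their countries", and the Trial 2 rationale describes valproate in similar terms for generalised seizures. Prior AED is not a stratification factor (section 6.3 names country, age and sex). Randomisation would still balance pre-started patients on average, and a rule tied to allocation undoes that balance. Section 9.6 gives the per-protocol analysis the task of testing the robustness of the intention-to-treat result, so a difference between the two could partly reflect local prescribing.

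**Working it through.** **Reading the passages together.** Take two identical Trial 1 patients who have each had 5 days of carbamazepine.

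| Allocated drug | Section 7.1 | Section 9.1 | Section 9.6, literal | Section 9.6, only use after randomisation counted |
|---|---|---|---|---|
| Carbamazepine | continue | kept | kept | kept |
| Levetiracetam, no overlap | stop carbamazepine | kept | dropped | kept |
| Levetiracetam, brief overlap | stop carbamazepine after overlap | kept | dropped | dropped |

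Every row complies with the protocol. Sections 9.1 and 9.6 disagree in the third row on either reading, and in the second row on the literal one.

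**Inputs for an illustration.** The plan states no figure on this point, so there is none to reproduce.

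- From section 9.2: 489 patients per arm in Trial 1, 253 per arm in Trial 2, and a 67% remission rate (the lamotrigine figure for focal seizures, used here for every arm so that the drugs are equal).
- Assumed, because the protocol does not give them: the share pre-started, f = 5%, 10% or 20%; the starter mix, with share s in a given arm's own drug; and remission 15 points lower in pre-started patients, whatever the starter drug.

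**Expected removals in an arm (literal reading)** = arm size × f × (1 − s).

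- Trial 1, all starters on carbamazepine: 489 × 0.05 = 24 to 489 × 0.20 = 98 from each of the levetiracetam and lamotrigine arms, and 0 from carbamazepine.
- Trial 1, f = 10%, starters 60% carbamazepine, 20% levetiracetam, 20% lamotrigine: 489 × 0.10 × 0.8 = 39, 39, and 489 × 0.10 × 0.4 = 20 from carbamazepine.
- Trial 1, f = 10%, even thirds: 33 from each arm. Starters on a drug outside the trial: 49 from each arm.
- Trial 2, f = 10%: 25 levetiracetam and 0 valproate if all start on valproate; 18 and 8 with a 70/30 valproate/levetiracetam mix; 13 and 13 with 50/50.

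**Effect on the Trial 1 per-protocol rate.** Let r = f × (1 − s) be the fraction of an arm removed. If the arm as a whole remits at 67%, pre-started patients remit at 67 − 15(1 − f). The rate among those left is 67 + 15(1 − f) × r/(1 − r).

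| f | Starter mix | Levetiracetam or lamotrigine | Carbamazepine | Spurious difference |
|---|---|---|---|---|
| 5% | 60/20/20 | 67.59 (r = 0.04) | 67.29 (r = 0.02) | 0.3 |
| 10% | 60/20/20 | 68.17 (r = 0.08) | 67.56 (r = 0.04) | 0.6 |
| 20% | 60/20/20 | 69.29 (r = 0.16) | 68.04 (r = 0.08) | 1.2 |
| 5% | all carbamazepine | 67.75 (r = 0.05) | 67.00 (r = 0) | 0.8 |
| 10% | all carbamazepine | 68.50 (r = 0.10) | 67.00 (r = 0) | 1.5 |
| 20% | all carbamazepine | 70.00 (r = 0.20) | 67.00 (r = 0) | 3.0 |

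With even thirds, or a starter drug outside the trial, r is the same in every arm and the difference is 0. If only use after randomisation counts, r shrinks to the fraction who overlap, which the protocol does not give. On the same 15-point gap, the table is then an upper limit.

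**The case against.** The best defence is that the rule has a natural start. The endpoint clock runs from randomisation, so use that ended earlier could be taken to fall outside it. Section 7.1 also expects the earlier drug to be stopped at once in most cases. On that view only the minority who overlap are caught. This reading is reasonable and reduces the problem, but section 9.6 does not state it, and it still drops compliant patients who overlap.

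A second defence is that section 9.1 would keep these patients, that the Trial Steering Committee decides exclusions, and that a full SAP is to follow. However, section 9.6 is the more specific text and already fixes the rule. The committee is to be blinded to allocation, so it cannot itself tell whether a drug differs from the one allocated. The protocol therefore gives two answers, which is more than a detail left open.

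A reader might go further than the text allows in three ways:

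- That patients are necessarily removed in unequal numbers. Numbers are equal with an even spread of trial drugs, though the arms then still differ in which starters remain, and equal when the prior drug is outside the trial. The remarks on first-choice drugs describe local opinion, not what recruits had been started on.
- That the bias is about 3 points. That needs 20% pre-started, all on carbamazepine, and a 15-point gap. The protocol supports none of these figures and does not say that pre-started patients do worse. If they did better, the direction would reverse.
- That secondary endpoint 4.2(g) has the same fault. Its wording on changing to another AED most naturally means leaving the allocated drug, and no contradiction appears there.

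**Conclusion.** The point holds as an inconsistency between sections 9.6, 9.1 and 7.1. As worded, 9.6 makes exclusion of some compliant patients depend on allocation, and even the narrower reading leaves the overlap cases.

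Bias needs two further conditions: an uneven spread of starter drugs, and a different prognosis in pre-started patients. Its size cannot be determined from the protocol. Under the stated assumptions it is about 0.3-1.2 points with a 60/20/20 mix and up to 0.8-3.0 points in the extreme mix, against the 10-point minimum important difference in section 9.2. It approaches zero if few patients enter pre-treated or if prognosis does not differ.

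Only the secondary per-protocol analysis is touched. The primary analysis includes all randomised patients by intention to treat and is unaffected. This is a minor correction.

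**What to change.** Add one clause to section 9.6, and align section 9.1 with it. For the rule on taking a different AED, use of an AED before randomisation, and the switch from it as permitted by section 7.1, does not count. A patient who does not complete the switch to the allocated drug, or who takes another different AED after randomisation and before the primary endpoint, is still excluded. With this clause, removals of compliant patients by this route fall to 0 in every arm.

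Two tempting variants should be avoided. Counting only AEDs newly started after randomisation would keep a patient who never stops the starter drug. Adjusting for whether the starter drug was the same as or different from the one allocated is not a baseline adjustment, because the category depends on allocation. Section 4.2(g) needs no change.

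The cost is one sentence before analysis. Section 7.1 already requires the start and stop dates, so no new data are needed.

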#### 4. TRIAL DESIGN

# 4.1 Primary Endpoint

The primary endpoint for each of the 5 EpiNet-*First* trials is time to 12 month remission from seizures; the time (T0) will start from the date of randomisation, even if the patient commences the AED on another day. (The time will be taken from the date of randomisation, rather than the date of the last seizure which preceded randomisation.)

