# 4.2 Secondary Endpoint(s)

- a. Time to treatment failure, due to either inadequate seizure control, or due to unacceptable adverse events. Treatment failure due to inadequate seizure control will have occurred when the clinician and/or patient decide that treatment withdrawal, or the addition of a second antiepileptic drug is required due to the occurrence of a seizure on the maximum recommended dose of randomised drug, or the maximum tolerated dose of the drug; treatment failure due to unacceptable adverse events will have occurred when the patient experiences adverse events attributed to the drug necessitating its withdrawal.
- b. Time to treatment failure due to inadequate seizure control.
- c. Time to treatment failure due to unacceptable adverse events.
- d. Time to first seizure;
- e. Time to 24 month remission;
- f. Serious Adverse events attributed to the trial medication or other anti-epileptic medication;
- g. Proportion of patients who achieve a 12 month remission by 18 months who have not changed to a different AED;
- h. Quality of life (QOL) (assessed using QOLIE31)(37)

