# 5.3 Cessation/Change of AED Treatment, Patient Transfer and Withdrawal

In consenting to the trial, patients are consenting to trial treatment, follow-up and data collection. If withdrawal of the randomly allocated treatment occurs, patients should still be followed up to allow a thorough assessment of the treatment policies, as patients may still achieve the primary outcome (12 month remission) following withdrawal of randomised treatment.

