#### 9. STATISTICAL CONSIDERATIONS

#### 9.1 Introduction

Statistical analyses will be performed on each individual trial separately, using SAS version 9.3 (SAS Institute Inc. Cary NC). Trial data will be collected using the EpiNet web-based database, and extracted into SAS for data quality checks and final statistical analysis when all patients have a minimum two year follow-up data at the end of the trial.

All primary analyses of time to 12 month remission from seizures will be on an intention to treat (ITT) basis including all randomised patients regardless of whether they actually satisfied the entry criteria, the treatment actually received, and subsequent withdrawal or deviation from the protocol. Secondary per protocol (PP) analyses will also be undertaken to assess the robustness of ITT analyses. This analysis will include all randomised patients who have taken the prescribed study drug and who do not have major protocol violations. All statistical tests will be two-sided and a 5% significance level maintained throughout the analyses. Confidence intervals for all point estimates will be two-sided 95% intervals.

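### The per-protocol set in section 9.6 is defined partly by outcome-related events after randomisation, so its agreement or disagreement with ITT is not reliable evidence of robustness

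*Protocol*

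**What the plan says.** Protocol section 9.6 gives the purpose: "Secondary per protocol (PP) analyses will be undertaken to assess the robustness of ITT analyses". Apart from patients who prove not to have epilepsy or, in Trials 1 to 3, to have the wrong seizure class, it excludes two groups:

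- "patients who were lost to follow up or for whom there is inadequate data to determine if they reached the primary endpoint";
- "all patients who took a different AED from the drug to which they had been randomised, before reaching the primary endpoint".

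The Trial Steering Committee decides the exclusions and is a body "who will be blinded to the treatment allocation and outcome data for each patient".

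Other sections bear on this:

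- Section 9.1 describes the same set differently: "This analysis will include all randomised patients who have taken the prescribed study drug and who do not have major protocol violations".
- Section 4.1 makes the primary endpoint "time to 12 month remission from seizures", counted from randomisation.
- Section 4.2 defines failure for inadequate seizure control as the point at which "treatment withdrawal, or the addition of a second antiepileptic drug is required due to the occurrence of a seizure" on the maximum recommended or tolerated dose. Withdrawal for adverse events is the other failure route.
- Sections 2.4.1, 5.3.1 and 7.7 allow the allocated drug to be changed. Section 5.3 keeps such patients in follow-up because "patients may still achieve the primary outcome (12 month remission) following withdrawal of randomised treatment".

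**The concern.** A permitted change of drug is not a departure from the protocol. It is mostly the event that section 4.2 calls treatment failure. Section 9.6 removes a patient if the change comes before remission and keeps the patient if it comes after, so membership depends on the timing of the outcome. Twelve-month remission cannot occur before month 12, so every patient is exposed to the rule for the first year. After that, only patients not yet in remission are exposed.

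If one drug controls seizures less well and more of its patients change drug, the rule strips that arm of poor responders and leaves it looking better. Deleting patients lost before remission works in the same direction within an arm, because it removes only event-free time. The Kaplan-Meier and log-rank methods of section 9.5 could have used that time as censored.

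At stake is the reading of the robustness check. A discrepancy could be taken to undermine a sound ITT result, or agreement to confirm an unsound one.

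**Working it through.** **Plan's own figure.** Section 9.6 gives none, so there is nothing to reproduce.

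**Inputs from the protocol (section 9.2).** 24-month remission in the earlier trials was 67% (lamotrigine) and 70% (carbamazepine) in focal epilepsy, and 73% (lamotrigine) in the generalised and unclassified group. The planned difference is 10 points.

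**Inputs assumed, because the protocol does not give them.** *s*, the share of an arm that takes a different drug before remission: 10% v 30%, and also 20% v 30%. *q*, the 24-month remission rate of those patients: 30% to 50%.

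**Formula.** Let *R* be the arm's remission rate with everyone kept. Removing the switchers gives

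PP = (R − s·q) / (1 − s).

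With the same *R* and *q* in both arms, the gap between arms is

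(R − q) × [1/(1 − s₂) − 1/(1 − s₁)].

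**Equal true remission, R = 0.67, q = 0.40.**

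- s = 0.10: (0.67 − 0.04)/0.90 = 70.0%
- s = 0.30: (0.67 − 0.12)/0.70 = 78.6%
- False gap: 8.6 points, in favour of the arm that switched more.

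**Range.** For 10% v 30% the bracket is 1/0.70 − 1/0.90 = 0.3175. For 20% v 30% it is 1/0.70 − 1/0.80 = 0.1786.

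| R | q | gap, 10% v 30% | gap, 20% v 30% |
|---|---|---|---|
| 0.67 | 0.50 | 0.17 × 0.3175 = 5.4 | 0.17 × 0.1786 = 3.0 |
| 0.67 | 0.40 | 0.27 × 0.3175 = 8.6 | 0.27 × 0.1786 = 4.8 |
| 0.67 | 0.30 | 0.37 × 0.3175 = 11.7 | 0.37 × 0.1786 = 6.6 |
| 0.73 | 0.50 | 0.23 × 0.3175 = 7.3 | 0.23 × 0.1786 = 4.1 |
| 0.73 | 0.30 | 0.43 × 0.3175 = 13.7 | 0.43 × 0.1786 = 7.7 |

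Gaps are in percentage points and come from unrounded rates. Subtracting rounded rates can shift the last digit, for example 82.9 − 71.1 = 11.8 in the third row.

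**A real difference can change sign.** Take R = 0.70 v 0.67, s = 0.10 v 0.30 and q = 0.40. ITT favours the first arm by 3 points. Per-protocol gives (0.70 − 0.04)/0.90 = 73.3% v 78.6%, which favours the second arm by 5.2 points.

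**When it does no harm.** The gap is zero if q = R, that is, if switchers remit as often as the rest of the arm. It is also zero if *s*, *R* and *q* are equal in both arms.

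**Blinding.** Whether another drug was taken can be handed to the committee as a yes/no flag, and inadequate data as a completeness flag. Whether the change came before remission is itself outcome information, so that criterion conflicts with outcome blinding unless someone else derives it first.

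**The case against.** The strongest reply is that only a secondary analysis is touched. These are superiority trials, and section 9.1 puts the primary analysis on all randomised patients whatever they took. Switched patients stay in follow-up. This stands, and it limits the severity.

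Part of the remedy is also planned already. Endpoint 4.2(g) counts remission by 18 months without a change of drug, and section 9.5 plans cumulative incidence by reason for treatment failure. This stands in part: neither repairs the set that section 9.6 presents as the robustness check.

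Four stronger readings are tempting, and the protocol does not support them:

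- *The bias always favours the drug abandoned more.* Switching for tolerability is one of the two failure routes. If it is unrelated to prognosis, the gap is near 0. Size and direction depend on why patients switch.
- *Every excluded switch is a treatment failure, so only responders and tolerators remain.* Section 4.2 requires a seizure on the maximum recommended or tolerated dose, and section 7.7 allows changes for other reasons. Patients who stop without starting another drug are not caught by the quoted exclusion.
- *A true difference is bound to shrink to zero.* That follows only if stayers are assumed to remit equally in both arms, which builds in the answer.
- *The rule cannot be applied blind at all.* The conflict is mainly with the timing criterion.

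An SAP could refine the set, but the protocol itself fixes this exclusion list, so deferral to an unseen SAP is not a full answer.

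**Conclusion.** The point holds as a weakness of a secondary analysis that should be fixed. Section 9.6 selects partly on outcome, and for events that the protocol permits. It also does not match section 9.1, under which a permitted change of drug is not a violation.

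Under the assumed switching rates of 10% v 30% and equal true remission of 67%, the false gap is 8.6 points at 40% remission in switchers, and 5.4 to 11.7 points over 50% to 30%. The planned difference is 10 points. With 20% v 30% switching the gap is 3.0 to 6.6 points. These sizes rest on rates that the protocol does not give, and on switching that is related to poor control and differs between arms.

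Neither agreement nor disagreement with ITT can be relied on as evidence of robustness. The primary ITT result is not called into question.

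**What to change.** Reword section 9.6 and align it with section 9.1:

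1. Limit per-protocol exclusions to entry status (not epilepsy; wrong seizure class in Trials 1 to 3) and to never having taken the allocated drug.
2. Keep lost patients and censor them at last contact.
3. Do not delete patients who switch or add a drug. Either keep them as in ITT, or censor at the change with inverse-probability-of-censoring weights.
4. If remission on randomised monotherapy is wanted, report it as a separate estimand with drug change as a competing event, extending endpoint 4.2(g). It is not a check of ITT. For example, assume that 20% v 40% change drug and that 85% of stayers and 50% of changers remit. ITT is then 0.80 × 85 + 0.20 × 50 = 78% v 0.60 × 85 + 0.40 × 50 = 71%, a gap of 7 points. Counting changers as non-remitters gives 0.80 × 85 = 68% v 0.60 × 85 = 51%, a gap of 17 points.
5. Let the blinded committee rule on entry diagnosis only, with never having taken the allocated drug supplied as a yes/no flag. This removes the conflict with outcome blinding.

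The cost is a rewording before any data are analysed and, if chosen, one weighted or competing-risk analysis. Drug changes, their reasons and seizure dates are already recorded.

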Participants will be randomised from within the EpiNet database, using a secure (24-hour) web based randomisation programme. Personal login username and password will be required to access the EpiNet database and the web-based randomisation system. When eligibility has been confirmed the participant will be randomised. Treatment allocation will be displayed to the authorised randomiser on a secure webpage within the EpiNet record, and an automated email confirmation will be sent to the authorised EpiNet investigator, PI and the trial coordinator.

If there are any problems with the randomisation systems, please contact the EpiNet-First coordination service via e-mail: [contact]

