# 7.4 Unblinding

EpiNet-First trials are open-label trials and therefore unblinding is not required.

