# **15. TRIAL COMMITTEE**

# 15.1 Trial Steering Committee (TSC)

The Trial Steering Committee will comprise members of the EpiNet steering committee plus a biostatistician and the principal Investigators from several of the countries in which the EpiNet trials will be run. The role of the TSC is to provide overall supervision for the trial. The ultimate decision for the continuation of the trial lies with the TSC.

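### The blinding that section 9.6 claims for the steering committee's per-protocol exclusions cannot hold as written: two of the five grounds need endpoint information, and one of those also needs the allocated drug

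*Protocol*

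**What the plan says.** Section 9.6 of the protocol makes the per-protocol analysis a secondary check on the robustness of the intention-to-treat result. It assigns the choice of exclusions to the TSC, "who will be blinded to the treatment allocation and outcome data for each patient".

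The same section sets five grounds for exclusion:

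- "patients who turned out not to have epilepsy";
- patients lost to follow-up;
- patients "for whom there is inadequate data to determine if they reached the primary endpoint";
- "all patients who took a different AED from the drug to which they had been randomised, before reaching the primary endpoint";
- patients with the wrong seizure type for their trial. In Trial 1 these are patients "who turned out not to have focal seizures will be excluded from the PP analysis", with a matching rule for focal seizures in Trials 2 and 3.

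Three other sections bear on the claim. Section 7.4 says "EpiNet-First trials are open-label trials and therefore unblinding is not required". Section 15.1 puts on the TSC, besides the EpiNet steering committee and a biostatistician, "the principal Investigators from several of the countries in which the EpiNet trials will be run". Section 6.3 says that at randomisation "an automated email confirmation will be sent to the authorised EpiNet investigator, PI and the trial coordinator".

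**The concern.** The blinding statement covers every exclusion and every patient, yet some of the exclusion rules turn on the very facts to be hidden. Part of the committee is also drawn from investigators in an open-label trial.

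What is at stake is the credibility of the per-protocol analysis as a check. Whether a patient had epilepsy, or focal seizures, is a judgement. If the people making it can see the drug and the course of seizures, that knowledge can influence who leaves which arm. A report that repeated the sentence in section 9.6 would also claim a protection that the trial, as described, did not have.

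**Working it through.** No sample size, event count or error rate enters this point, so there is nothing to calculate. The check is to ask of each ground in section 9.6 what must be known to apply it.

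| Ground | Needs allocation? | Needs outcome? |
|---|---|---|
| Not epilepsy | No | No, not remission status |
| Lost to follow-up | No | Only as contact status |
| Endpoint cannot be determined | No | Yes, endpoint status |
| Different AED before the endpoint | Yes | Yes, endpoint timing |
| Wrong seizure type (Trials 1 to 3) | No | No, though it may draw on seizures described in follow-up |

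So one ground of five needs both allocation and outcome, one more needs endpoint status, and three can be applied without allocation or remission status.

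**The different-AED ground.** Applying it takes two comparisons: drug taken against drug randomised, and date of switch against date of the primary endpoint (12-month remission, section 4.1). Suppose someone else makes these comparisons and passes the TSC a bare yes/no flag. The arm is then hidden, but a yes still shows that the patient had not reached 12-month remission when the drug was changed. It does not reveal the final outcome, since section 5.3 notes that remission may still follow a switch. It is outcome information all the same, so blinding to outcome fails for those patients.

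**The inadequate-data ground.** Someone must establish whether the endpoint can be ascertained. Whoever applies the rule learns that much about the outcome.

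**The committee.** Section 6.3 sends each allocation to the investigator and the PI. Section 12.3 has the arm written in the medical record. Section 12.2 requires an accredited investigator at the site to verify the data before they enter the research database. A TSC member who recruits or follows trial patients would therefore know the drug, and probably the course, of those patients. That such members do so is a strong inference from sections 6.3 and 15.1; neither section says it outright.

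**What the protocol provides.** It names no one to derive masked flags, describes no redaction step, and has no rule that a member stands aside for his or her own patients.

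**The case against.** The strongest reply is that a blinded data review is feasible and that its mechanics belong in the SAP. Section 9.5 promises a full SAP, agreed by the TSC and then sent to the Independent Advisory Group. A project statistician (section 9.5) and an independent data analyst (section 12.4) are available to prepare a masked file. Nothing in the protocol says that TSC members will be shown whole records from other centres. Diagnosis and seizure class can also change on EEG or imaging results that arrive after randomisation (section 6.2), and those reveal neither drug nor remission. Finally, the per-protocol analysis is secondary.

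Much of this stands, and it rules out four stronger readings that a reader might infer:

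- That all the exclusion rules need both allocation and outcome. Only one of the five does.
- That blinded exclusion is impossible. With mechanical flags derived elsewhere and a masked extract, blinding to allocation is achievable for the diagnostic grounds, and blinding to outcome largely so.
- That the committee is unblinded throughout. Members' knowledge is an inference, and it extends to their own patients, not to every patient.
- That the main result is compromised. Section 9.1 bases the primary analysis on all randomised patients.

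What does not stand is the appeal to the SAP as a full answer. The point is not a missing detail. The protocol itself fixes who decides, fixes the membership, and asserts full blinding for each patient. A SAP could add masking, but the sentence in section 9.6 would remain inaccurate for the two endpoint-dependent grounds.

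**Conclusion.** The point holds in limited form. The blinding described in section 9.6 is not a property of the design as written. It conflicts outright with one ground (different AED before the endpoint), conflicts on outcome with a second (undetermined endpoint), and very probably fails for members' own patients. The remaining three grounds can be applied without allocation.

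The consequence is confined to the secondary per-protocol analysis. The protocol gives no figure for how many patients would fall under each ground, so the possible bias cannot be sized; selective reclassification is a route left open, not a demonstrated effect. The conclusion rests on reading the blinding sentence as covering every exclusion, which is how it is worded. The part about members also assumes that the principal investigators on the TSC treat trial patients or receive their allocations. The correction should be made because it is cheap and puts right a stated safeguard.

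**What to change.** Amend section 9.6 in four respects.

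1. The statistician derives the mechanical grounds (different AED before the endpoint, undetermined endpoint, loss to follow-up) from the database by a fixed rule, with no TSC decision.
2. The TSC decides only the diagnostic grounds (not epilepsy, wrong seizure class). It works from an extract that omits allocation, AED names and remission status but keeps the clinical, EEG and imaging information needed for a diagnosis. Removing all seizure dates and counts would go too far, because eligibility itself rests on two or more spontaneous seizures (section 5.1). The decisions are locked before the analysis.
3. Members stand aside for patients under their own care or at their own site. Abstention for a whole country is not needed.
4. The blinding statement is reworded to cover step 2 only.

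The cost is a change of wording, one masked extract and a narrower blinding claim. There is no added burden on patients.
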